2.6.1.2. PFS

As defined in section 2.4.2.2, PFS will be calculated as:

PFS (in months) = [date of event or censoring - first dose of treatment + 1]/30.4375.

PFS will be calculated with one decimal.

2.6.2. Phases I and II

Exploratory endpoints below are common to both Phase I and Phase II. They will be assessed separately for Phase I and Phase II and by disease group.

2.6.2.1. Immunological effects of hu3F8-BsAb

Lymphocyte subsets (including CD3, CD4, CD8, Foxp3, CD127, CD45RA, CCR7) and T cell activation/exhaustion markers (including CD25, PD-1) will be tested before and after the hu3F8-BsAb treatment. Each draw will collect about 16 mL of serum. Analysis will be performed in the Memorial Sloan Kettering (MSK) Immune Monitoring Core Facility. CBC should be checked with blood collected on the same day. Cytokine levels (including IFN-y, IL-6, IL-8, IL-10) will be measured before and after the hu3F8-BsAb treatment during cycle 1 of phase I, and analyzed in the MSK Immune Monitoring Core Facility. During subsequent

cycles of phase I or in phase II, these cytokine levels will be measured if CRS is clinically suspected. Each draw for cytokine levels will collect about 4mL of serum.

Lymphocytes from heparinized blood will be collected for lymphocyte subset markers (including CD3, CD4, CD8, Foxp3, CD127, CD45RA, CCR7) and T cell activation/exhaustion markers (including CD25 and PD-1).

- Phase I Cycle 1: On Days 2, 8 (prior to hu3F8-BsAb), 9, 10 and 11, and approximately Days 15 and 28.
- For subsequent cycles in phase I, and phase II: Before each dose of hu3F8-BsAb.

2.6.2.2. Tumor DNA, RNA for NB patients only

For NB patients, tumor RNA will be used for transcriptome and microRNA profiling. Tumor RNA in BM from blood will be used for Minimal Residual Disease (MRD) testing, to be completed in the [name] Lab at MSK. The samples will not have any associated patient-specific identifying information, but will be linked to clinical information such as patient age, gender, tumor stage, tumor recurrence status, and tumor site. Frozen tumors will be tested for tissue antigens and gangliosides (including but not limited to Disialotetrahexosylganglioside (GM2), GD2, Ganglioside Precursor Disialohematoside (GD3)).

2.6.2.3. Stool Microbiome

Based on emerging data on the impact of stool microbiome on function of immunotherapeutic agents, a stool sample will be collected on all patients prior to first dose of hu3F8-BsAb, where feasible.

2.6.2.4. Disease Control Rate (DCR) at Cycle 4

DCR is defined as :

- patients whose BOR at cycle 4 is CR, PR, MR or Stable Disease using INRC
- patients whose BOR at cycle 4 is CR, PR or Stable Disease, using RECIST v1.1.

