- **10.15** Lymphocytes from heparinized blood will be collected for lymphocyte subset markers (including CD3, CD4, CD8, Foxp3, CD127, CD45RA, CCR7) and T cell activation/exhaustion markers (including CD25 and PD-1).

- Phase I Cycle 1: On Days 2, 8 (prior to hu3F8-BsAb), 9, 10 and 11, and approximately Days 15 and 28.
- For subsequent cycles in phase I, and phase II: Before each dose of hu3F8-BsAb.
- **10.16** For patients with a diagnosis of neuroblastoma, the following studies will be performed any time after the second dose of hu3F8-BsAb in cycle 2 and cycle 4, and then approximately every 3 months while on study:
 - BM aspirates and biopsies from bilateral iliac crests for standard histochemical studies, as well as for immunocytology and other molecular markers of disseminated NB.
 - Imaging by computed tomography (CT) or magnetic resonance imaging (MRI) of primary tumor site, plus metaiodobenzylguanidine (MIBG) scan or positron emission tomography (PET).
- **10.17** For patients with osteosarcoma or GD2(+) tumors, the following studies will be performed any time after the second dose of hu3F8-BsAb in cycle 2 and cycle 4*, and then approximately every 3 months while on study:
 - Disease evaluations with imaging by computed tomography (CT) or magnetic resonance imaging (MRI) of primary tumor site and/or known site(s) of relapse (if applicable), with/without positron emission tomography (PET) or bone scan, or other diagnostic imaging as appropriate for specific disease.

*Cycle 4 scans should occur at approximately 4 months (+/- 1 month) in order for scans to be used to evaluate the 4 month disease control rate (see section 14.2.1.2).

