2.1.2. Phase II

After RP2D is determined, a phase II trial will be carried out to assess the anti-tumor activity of hu3F8-BsAb. Two groups of patients will be studied: Group 1 will consist of patients with relapsed or refractory NB and Group 2 of relapsed or refractory measurable osteosarcoma. Hu3F8-BsAb is given on Days 1 and 8 of each cycle. The duration of each cycle is 28 days. However, cycles may be delayed for up to 56 days if >grade 2 toxicity is encountered.

HAHA titer will be measured after each cycle. If HAHA develops, cycles are deferred for up to 120 days until HAHA titer <1300 U/ml. Extent of Disease Evaluation (EOD) will be performed after the second dose of cycle 2 and cycle 4, then every 3 months thereafter.

A total of 4 cycles will be given, and patients with no life-threatening toxicity clearly attributable to hu3F8-BsAb, no progressive disease, continuing to meet all eligibility criteria and HAHA titer is <1300U/ml have the option of receiving additional cycles up to 2 years from the start of the Hu3F8-BsAb treatment. Patients may continue therapy beyond 4 cycles even if they achieve remission.

After cycle 4, duration between cycles can range from 28-120 days. Patients will undergo physical examination, Complete Blood Count (CBC) and complete chemistry and immune correlates will be tested as described in Protocol Section 10.

For Group 1, the overall response rate will be evaluated and is defined as the proportion of patients achieving Complete Remission (CR) or Partial Response (PR) based on revised International Neuroblastoma Response Criteria (INRC)³ as the best of the responses at the end of cycle 2 and cycle 4. (See Section 2.4.2.1) excluding potential response assessments after initiation of any new prohibited anticancer treatment).

For Group 2, 4-month Progression Free Survival (PFS) will be assessed and is defined as the proportion of patients who have not developed progressive disease nor died at the end of 4 months from the first dose of Hu3F8-BsAb. In addition, number of patients who have CR or PR as the best of the responses at the end of cycle 2 and cycle 4 will be determined. (see Section 2.5.2.2)

Hu3F8-BsAb is given IV over ~1-3 hours on Days 1 and 8 for each cycle.

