2.5.1.3. ORR

For NB, anti-tumor activity will be measured by revised INRC.

For osteosarcoma and other GD2(+) tumors, the response and progression will be evaluated in this trial using the RECIST Committee, version 1.1.

The proportion of NB, osteosarcoma, and other GD2(+) tumor patients responding to therapy will be determined for each disease type.

ORR will be defined as the proportion of patients achieving CR or PR as BOR at the end of cycle 4.

In addition, a similar analysis will be performed corresponding to end of trial but before any new prohibited anticancer therapy intakes. Potential response assessments after initiation of any new prohibited anticancer treatment will not be included in the assessment of BOR.

Thus, the BOR will be the best response recorded from the initiation to the following timepoints:

- At the end of cycle 4
- At the end of the trial.

For patients with osteosarcoma and other GD2(+) tumors, each patient will be assigned one of the following categories: CR, PR, Stable Disease, Progressive Disease, Not Evaluable (NE).

Patients' response will also be classified as "unknown" if insufficient data were collected to allow evaluation per these criteria.

According to RECIST v1.1, the following table provides a summary of the overall response status calculation at each time point for patients with or without measurable disease at baseline:

Target Lesions	Non-Target Lesions	New Lesions	Overall Response
CR	CR	No	CR
CR	Non-CR/Non-Progressive Disease	No	PR
CR	Not all evaluated	No	PR
PR	Non-Progressive Disease / not all evaluated	No	PR
Stable Disease	Non-Progressive Disease / not all evaluated	No	Stable Disease
Not all evaluated	Non-Progressive Disease	No	NE
Progressive Disease	Any	Any	Progressive Disease
Any	Progressive Disease	Any	Progressive Disease
Any	Any	Yes	Progressive Disease

Table 4 Integration of target, non-target and new lesions into response assessment

Note: Patients with a global deterioration of health status requiring discontinuation of treatment without objective evidence of disease progression (or evidence of unequivocal disease progression) at that time should be reported as "*symptomatic deterioration*". This is a reason for stopping therapy, but is NOT objective Progressive Disease. Every effort should be made to document the objective progression even after discontinuation of treatment.

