The overall response will be determined for all protocol specified assessments, ie scheduled assessments (with or without missing information) and also for all unscheduled assessments with non-missing information.

If a scheduled assessment is completely missing (target, non-target, new lesion), the overall response will be NE.

When Stable Disease is believed to be the BOR, it needs to be assessed a minimum of 6 weeks (+/- 7 days) after start of treatment. Otherwise, the BOR will be NE, unless any Progressive Disease was further documented, in which case BOR will be Progressive Disease.

If a patient progressed before this first assessment, he will be considered as 'early progressive'. If this event occurs, the overall response of the patient will be presumed as progression. This corresponds to patient who withdraws without any scan and whose reason for ending treatment or ending study is progressive disease (according to investigator opinion). In case of patient with a reason different to progressive disease, he will not be considered as progressive disease but will be at least considered as non-responder.

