5.1.4. Visit Windows

All data will be analyzed using nominal trial visit as defined in Table 2 and Table 3 (see section 2.1.3) and eCRF. No visit windows will be applied for summary and analysis except for scan assessments for which the following visit windows will be considered:

- Cycle 2: 61 days +/- 30 days
- Cycle 4: 122 days +/- 30 days

For scans after cycle 4, supposed to occur every 3 months, the visit windows will be calculated using the date of the previous scan. For example:

- For the first scan after cycle 4, the windows will be: Cycle 4 scan date + 91 days (3 months) +/- 30 days;
- For the second scan after cycle 4, the windows will be: Date of first scan after cycle 4
 + 91 days +/- 30 days; and so on for the next scans...

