6.6.3.6.1. Additional analyses HAHA for Phase I

HAHA titer value over time will be presented graphically with time of dosing for patients in the Safety Analysis Set.

In addition, the correlation between HAHA response and ORR after cycle 4 (for neuroblastoma patients) will be analyzed using a logistic regression with inclusion of log(therapeutic dose) as a covariate and whether patients have HAHA at any point up until the last pre-dose HAHA assessment before cycle 4. If patients have switched dose after cycle 2, the average therapeutic dose will be used.

Similar analysis will be performed with DCR after cycle 4 (for osteosarcoma patients).

The association between HAHA and OS and PFS up to 4 months will be analysed by cancer type group using Cox-Regression analyses with log(therapeutic dose) and HAHA (Yes/ No) as time-dependent covariates. These analyses will be based on patients from the FAS.

This information will be summarized separately by cancer type in patients.

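### SAP 2.6.2.4 defines disease control at Cycle 4 by best overall response, so stable disease at cycle 2 followed by progression at cycle 4 counts as controlled

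*SAP*

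**What the plan says.** SAP 2.6.2.4, headed as the DCR at Cycle 4, has two bullets. Under RECIST it counts "patients whose BOR at cycle 4 is CR, PR or Stable Disease, using RECIST v1.1". Under INRC it counts "patients whose BOR at cycle 4 is CR, PR, MR or Stable Disease using INRC". It does not say where BOR is defined.

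The full definition is in SAP 2.5.1.3, the Phase I ORR section: "Thus, the BOR will be the best response recorded from the initiation to the following timepoints", which are the end of cycle 4 and the end of the trial. For SD to be the BOR, "it needs to be assessed a minimum of 6 weeks (+/- 7 days) after start of treatment". For Phase II response, SAP 2.1.2 uses the "best of the responses at the end of cycle 2 and cycle 4". SAP 2.4.2.1 words BOR more briefly, as the best response at the end of cycle 4.

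Protocol 10.17 asks for the cycle 4 scan at about 4 months, give or take one month, "in order for scans to be used to evaluate the 4 month disease control rate", and refers the reader to Protocol 14.2.1.2. That section sets out the 4-month PFS endpoint for osteosarcoma. Protocol 4.1.2 defines that endpoint as not having progressed by 4 months.

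DCR is used in two places. SAP 6.6.6.6 reports it with Wilson intervals for Phase I and Phase II. SAP 6.6.3.6.1, on HAHA in Phase I, says: "Similar analysis will be performed with DCR after cycle 4 (for osteosarcoma patients".

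**The concern.** The name of the endpoint promises the patient's status at cycle 4. The definition gives the best status reached at any time up to then. Once a patient has a qualifying SD at cycle 2, the cycle 4 scan cannot undo it, although the protocol times that scan to assess disease control at 4 months.

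Three things follow.

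- A Group 2 patient who progresses by 4 months can be a failure on the primary endpoint and a success on DCR at Cycle 4 in the same report.
- A patient with SD at cycle 2 and no cycle 4 scan also counts as controlled. The missing-data rule in SAP 5.2.1 covers ORR and PFS only.
- In the Phase I HAHA logistic model for osteosarcoma, HAHA is counted up to the last pre-dose sample before cycle 4, but the outcome may already be settled at cycle 2. HAHA that appears afterwards would be modelled as a predictor of something that preceded it.

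**Working it through.** The documents give no expected DCR, sample size or power for it, so there is no planned figure to reproduce. The check applies the SAP's own rules to one sequence of scans and then gives a rough scale.

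**Timing inputs**

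- Second dose of cycle 2: day 28 + 8 = 36. The scan follows it (Protocol 10.16 and 10.17).
- Cycle 2 scan window, SAP 5.1.4: "Cycle 2: 61 days +/- 30 days", that is days 31 to 91.
- Cycle 4 scan window, SAP 5.1.4: 122 ± 30, that is days 92 to 152.
- Earliest SD that can be the BOR, SAP 2.5.1.3: 42 − 7 = day 35 with the tolerance, day 42 without it.

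**Sequence: SD at cycle 2, progression at cycle 4**

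| Day of cycle 2 scan | SD qualifies (from day 35)? | BOR to end of cycle 4 | Counted in DCR |
|---|---|---|---|
| 33 | no | progression | not controlled |
| 36 | yes | SD | controlled |
| 42 | yes | SD | controlled |
| 61 | yes | SD | controlled |
| 91 | yes | SD | controlled |

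Only an SD before day 35 is overridden by the later progression, and that is earlier than the nominal second dose of cycle 2. Without the 7-day tolerance, scans on days 36 to 41 would not qualify, but days 42 to 91 still would. Under INRC, a mixed response at cycle 2 followed by progression is also counted as controlled.

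**Direction.** Anyone with CR, PR, SD (or MR under INRC) at the cycle 4 scan has a BOR at least that good. The BOR-based rate is therefore never below the rate by cycle 4 status.

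**Scale (illustration only).** Assume exponential PFS, S(t) = S(122)^(t/122), with S(122) set to the two 4-month rates in Protocol 14.2.1.2: 12% (historical and null) and 40% (alternative).

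| Cycle 2 scan on day | Progression-free if S(122) = 12% | Progression-free if S(122) = 40% |
|---|---|---|
| 36 | 0.12^(36/122) = 54% | 0.40^(36/122) = 76% |
| 61 | 0.12^(61/122) = 35% | 0.40^(61/122) = 63% |
| 91 | 0.12^(91/122) = 21% | 0.40^(91/122) = 51% |

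These are ceilings on what can count through cycle 2 status, because they ignore missing and non-evaluable scans. The comparator moves too. With S(122) = 12%, the share progression-free at the start of the cycle 4 window is 0.12^(92/122) = 20%. A day-61 cycle 2 scan then gives a ratio of 34.6/20.2 = 1.7, against 34.6/12 = 2.9 when the cycle 4 scan is on day 122.

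**The case against.** The reading is likely but not certain. The cumulative definition and the six-week rule stand in the Phase I ORR section, SAP 2.6.2.4 does not point to them, and the shorter wording in SAP 2.4.2.1 could be taken as the response at the cycle 4 scan. Protocol 12.2 also treats progression at any time as a response failure. This stands as a limit, but it does not remove the point. The only full definition is the cumulative one, the SAP does not carry Protocol 12.2 into DCR, and two programmers could derive different rates.

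The protocol link is also loose. Protocol 10.17 points to a PFS endpoint, and the protocol gives no formula for DCR. A best-response DCR with the same cut-off as ORR would be a coherent choice; the fault would then be the label. SAP section 7 openly adds DCR as an exploratory endpoint. It is written against protocol version 8, while the protocol reviewed here is A(10), so the documents do not show whether the 10.17 note was in front of the SAP's authors. The two documents still differ as they stand.

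The 4-month question is largely answered elsewhere. Group 2's primary PFS counts such progressions as events. SAP 6.6.3.6.1 also relates HAHA to PFS up to 4 months by Cox regression with time-dependent covariates. Responses at each cycle are reported. All of this stands and keeps the point minor.

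A reader might infer that DCR will be judged against the 12% benchmark. The documents do not support that: 12% is attached only to Group 2 PFS, and SAP 6.6.6.6 gives DCR no null value or success rule.

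**Conclusion.** The point holds as a minor one about definition and labelling. On the SAP's only full definition of BOR, SD (or MR under INRC) at cycle 2 followed by progression at cycle 4 counts as disease control at Cycle 4. This departs from the purpose Protocol 10.17 gives the cycle 4 scan, and SAP section 7 does not list it.

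The effect is confined to the reported DCR, which can only equal or exceed the rate by cycle 4 status, and to the osteosarcoma outcome in the Phase I HAHA logistic model. No primary analysis or success decision changes.

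The upward direction follows from the rules, but the size does not. The figure of about 35% at a 12% 4-month rate (54% to 21% over scan days 36 to 91), or about 63% at 40%, rests on exponential PFS, which the documents do not state, and is an upper bound. It should not be read as a forecast of DCR or as a fixed multiple of 4-month control.

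**What to change.** In SAP 2.6.2.4, define DCR at Cycle 4 as CR, PR, SD or (INRC only) MR at the assessment in the cycle 4 window, with no earlier progression or death, and with a missing assessment counted as not controlled. Use the same variable in the HAHA logistic model in SAP 6.6.3.6.1.

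If a best-response measure is also wanted, report it separately under a name such as *best disease control through Cycle 4*, with a cross-reference to SAP 2.5.1.3 and an entry in section 7.

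The cost is one SAP sentence, plus the section 7 entry if both measures are kept. No new data are needed. The downside is that the reported DCR will be lower wherever a patient progresses, dies or misses the scan between cycle 2 and cycle 4.

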2.7. Safety Variable(s)

The following safety endpoints will be assessed:

- Adverse Events (AE)/ Serious Adverse Events (SAE), coded using the Medical Dictionary for Regulatory Activities (MedDRA) 23.1 and graded as per investigator judgement according to the NCI-CTCAE v4.0
- **Clinical laboratory** assessments as performed by local laboratories and entered in the eCRF by the site.
- Vital Signs
- Physical Examination

• Pain Assessment for phase I if evaluable

Pain scores will be assessed using the Face, Legs, Arms, Cry, Consolability (FLACC) scale ⁵,⁶ and/or the numeric scale⁷, as appropriate (see Appendix 2 for pain scales). Pain scores will be evaluated at the following time points on days with hu3F8-BsAb treatment:

- (a) once prior to commencement of any drug administration,
- (b) at least once during the acute pain episode when rescue pain medication doses are required (for hu3F8 this is towards the end of the 30 minute infusion or soon after completion of antibody infusion)
- (c) ~1 hour after the end of infusion or prior to discharge from the Pediatric Day Hospital.

Pain scores will be assessed for all treatment cycles. Opioid requirements, rather than pain score, will be used to establish safety for the Phase I primary objective (Section 2.2.1).

Pain scores will be used to assist clinical judgment (e.g. decision of pain medication use, observation of pain relief) and for documentation.

3. Estimand(s)

Not Applicable since no estimand was defined in the protocol.

4. Analysis Populations

In accordance with ICH E3 and E9⁸, the following analysis sets will be used for the analyses.

4.1. All Included Analysis Set

The all included analysis set will be defined as all patients who are not screening failures, and hence included in the trial. Screening failures who had been treated by mistake will also be in the all included analysis set

4.2. All Screened Set

The All Screened Set will include every patient who has signed the informed consent form. The All Screened Set will be used for summaries of disposition and the associated listing.

4.3. Full Analysis Set

The Full Analysis Set (FAS) will consist of all patients treated with at least one dose of treatment.

The FAS will be used for summaries and analysis of demographics and baseline characteristics, treatments and medications, secondary efficacy endpoints and will be the primary analysis set for the analysis of the primary efficacy endpoints (phase II analyses).

4.4. Safety Analysis Set

All patients treated with at least one dose of the treatment will be included in the Safety Analysis Set.

4.5. DLT Evaluable Analysis Set (DAS)

The DLT evaluable analysis set (DAS) is a subset of the SAF. This analysis population will include patients in the dose escalation phase who receive both doses of hu3F8-BsAb in cycle 1 and had sufficient safety evaluations, or who had a DLT during the DLT evaluation period.

4.6. Pharmacokinetics Analysis Set

The PK Analysis Set will include all patients who received at least 1 dose of treatment (Hu3F8-BsAb) and have at least 1 valid PK concentration.

4.7. Special Subpopulations

Not Applicable

5. Data Handling

5.1. Time Points and Visit Windows

5.1.1. General Definitions

All assessment days will be related to the first day of first dose of treatment.

Day 1 is defined as first dose of treatment. Relative days after Day 1 are calculated as (assessment date – Day 1 date) + 1. Relative days prior to Day 1 are calculated as (assessment date – Day 1 date). The day prior to Day 1 is Day -1. Day 0 is not defined.

The date of the first dose of treatment for each patient will be taken from the Drug Administration eCRF page. If the date in this eCRF page is missing, alternatively the date of corresponding visit date in the Visit Date eCRF page will be used.

The date of the last dose of treatment for each patient will be taken from the End of Treatment eCRF page. If the date in this eCRF page is missing, alternatively the last date of Drug Administration eCRF page will be used.

